1.2 Secondary Objectives

- Assess the safety and tolerability of Decitabine and Vorinostat followed by an infusion of CD3-/CD19- donor NK cells and a short course of IL-2 when given in the outpatient setting in patients with high risk MDS
- Assess the proportion of patients who become transfusion independent (red blood cells and/or platelets)
- Estimate the association of in vivo NK cell expansion with clinical response
- Estimate 1 year Overall Survival (OS)

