1.3 Correlative Laboratory Objectives

- Estimate the incidence of successful in vivo expansion of adoptively transferred haploidentical NK cells by NK cell persistence 2 weeks after infusion (Day 28)
- Monitor phenotypic and functional characteristics of natural killer cells and regulatory T cells in vivo

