2.1.4 Vorinostat Use as an Immunosuppressant

Vorinostat has also recently been cited as a possible immune modulating drug as evidence by elegant mouse work published by Reddy et al. In their mouse models of acute graft versus host disease of allogeneic stem cell transplantation, they showed that administration of Vorinostat soon after infusion of allogeneic stem cells, diminished inflammatory cytokines and subsequent development of acute graft versus host disease, while not impairing T cell responses to host antigens after transplant.³⁴

[figure not shown]
2.2 History of Adoptive NK Cell Therapy for Refractory/Relapsed AML at the U of MN

Using the platform of lymphodepletion with cyclophosphamide, fludarabine with subsequent infusion of CD3 depleted haploidentical natural killer cells and subsequent high dose IL-2 administration, we have treated total of 32 high risk refractory AML patients with the exact same therapy and NK cell enriched products at the University of Minnesota. A total of 10 of these patients achieved a complete remission. Of the ten patients achieving a remission three went on to get a subsequent allogeneic transplant and all had 2-year disease free survival.³⁵ Three patients died of toxicity. Four patients who were ineligible to go on to allogeneic transplant ultimately relapsed four to eleven months after achieving remission under this protocol. Morbidity associated with this regimen included a very prolonged hospital stay, on average of 4-6 weeks, as well as high fevers, capillary leak with pulmonary edema and peripheral edema, renal toxicity, etc with the high doses of IL-2 used. However, important to note that prolonged hospital admissions with potential higher toxicity is not uncommon for AML patients undergoing salvage chemotherapy. Although the outcomes were relatively favorable for patients with refractory leukemia, the transient nature of response in the absence of definitive therapy such as stem cell transplant and the associated high morbidity indicates that this adoptive cell therapy in its current form was not curative, at least in AML, and would likely be too high risk for an older cohort of MDS patients.

In Vivo Expansion Correlates With Increasing The Intensity Of The Preparative Regimen

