4.0 Selection of Patients

Study entry is open to adults regardless of gender or ethnic background. While there will be every effort to seek out and include females and minority patients, the patient population is expected to be no different than that of other studies of high risk myelodysplastic syndromes at the University of Minnesota and the Mayo Clinic.

Inclusion Criteria:

- 4.1 Diagnosis of high risk MDS that meets one of the following disease classifications and is requiring treatment:
 - 4.1.1 International Prognostic Scoring System (IPSS) Category: INT-2 or High Risk (see Appendix IV)
 - 4.1.2 International Prognostic Scoring System- Revised (IPSS-R) Category: High or Very High (Score of 5 or above) (Appendix IV)
 - 4.1.3 WHO Classification: RAEB-1 or RAEB-2 (Appendix V)
 - 4.1.4 WHO Classification: CMML that is not highly proliferative; WBC < 15k
 - 4.1.5 High risk cytogenetic abnormality as defined by presence of Monosomy 7, complex karyotype, or monosomal karyotype
 - 4.1.6 Therapy related MDS
 - 4.1.7 Severe cytopenias: Neutropenia (ANC \leq 0.8), platelet or PRBC transfusion dependent
 - 4.1.8 WHO Based Prognostic Scoring System (WPSS): High or Very High Risk (Appendix V)
- 4.2 Prior Treatment:
 - 4.2.1 Untreated/Minimally Treated: maximum of 2 cycles of hypomethylating agents (azacitidine or decitabine) without evidence of treatment failure as defined by progression to more advanced MDS Who classification or AML.

- 4.2.2** Treatment Failure: Patients who have not responded to or whose disease has progressed on hypomethylating agents (azacitidine or decitabine), 7+3 type induction chemotherapy, or immunosuppressive therapy such as ATG+CSA.
- 4.2.3** Patients must not have received treatment for their MDS within 4 weeks of beginning this study.
- 4.3** Age \geq 18 years of age
- 4.4** ECOG Performance Status 0-2 (Appendix III)
- 4.5** Available related HLA-haploidentical NK cell donor by at least Class I serologic typing at the A&B locus
- 4.6** Have acceptable organ function as defined below within 14 days (28 days for cardiac) of enrollment:
 - Renal: Creatinine: \leq 2.0 mg/dL
 - Hepatic: SGOT/SGPT $<$ 5 x upper limit of institutional normal (ULN)
 - Pulmonary: oxygen saturation \geq 90% on room air
 - Cardiac: LVEF by ECHO or MUGA \geq 40%, no uncontrolled angina, severe uncontrolled ventricular arrhythmias, or electrocardiographic evidence of acute ischemia or active conduction system abnormalities. QTc $<$ 500 msec

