9.0 Study Endpoints

This study is designed as a two stage study of the combination of Decitabine and Vorinostat and haploidentical NK cell infusion. The primary endpoint is clinical response (CR + PR + HI) at the end of the required 2 cycles of therapy. An assessment of response differences between untreated/minimally treated and those with prior treatment failures will be conducted.

The secondary endpoints include evaluation of safety tolerability, the proportion of patients who become transfusion independent, the association of the in vivo NK cell expansion with clinical response, and 1 year Overall Survival.

Clinical responses are defined in Appendix VI.

Determination of toxicities will be important for this new combination. As per NCI CTCAE Version 4.0, the term toxicity is defined as adverse events that are classified as either possibly, probably, or definitely related to study treatment. The maximum grade for each type of toxicity will be recorded for each patient, and frequency tables will be reviewed to determine toxicity patterns. In addition, we will review all adverse event data that is graded as 3, 4, or 5 and classified as either “unrelated or unlikely to be related” to study treatment in the event of an actual relationship developing.

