13.3 Statistical Analysis Methods

Ninety-five percent confidence intervals for the response probability were calculated using methodology reported by Duffy and Santner.⁴⁰

The summary statistics including 95% confidence intervals for toxicity rate and proportion of patients who become transfusion independent will be calculated. The association of in vivo NK cell expansion, as defined as persistence of donor NK cell chimerism at day +8, (yes or no) with clinical response will be estimated by chi-square test. Kaplan- Meier method will be used to estimate 1- year survival from the date of treatment. Given that the majority of patients will go on to receive additional therapy with either ongoing hypomethylating agents versus stem cell transplant, the estimates of 1 year overall survival from the point of study enrollment, will only be partially attributable to the study therapy and thus a minor focus of our statistical analysis.

SAS 9.2 (Cary, NC, USA) will be used for statistical analyses.

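### The NK-expansion/response association is to be estimated, but 13.3 gives only a pooled chi-square test: no effect size or interval, and no account of prior-treatment group

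*Combined protocol and SAP*

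**What the plan says.** Section 1.2 lists as a secondary objective: "Estimate the association of in vivo NK cell expansion with clinical response". The synopsis has the same aim, and section 9.0 repeats the association as a secondary endpoint.

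The only method is in section 13.3. Expansion is made binary, "as defined as persistence of donor NK cell chimerism at day +8, (yes or no"), and its association "with clinical response will be estimated by chi-square test". No effect measure, confidence interval, stratification or adjustment is given. The sentence just before it does specify intervals for other secondary outcomes: "The summary statistics including 95% confidence intervals for toxicity rate and proportion of patients who become transfusion independent will be calculated". The response probability also gets a 95% interval.

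Section 4.2 admits two prior-treatment groups. Criterion 4.2.1 covers untreated patients and those with a "maximum of 2 cycles of hypomethylating agents (azacitidine or decitabine) without evidence of treatment failure"; 4.2.2 covers treatment failures. On these groups section 9.0 says: "An assessment of response differences between untreated/minimally treated and those with prior treatment failures will be conducted". It gives no method and does not connect the groups to NK expansion.

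**The concern.** There are two gaps.

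**No estimate.** The objective asks how strong the association is. A chi-square test says only whether the data are surprising under no association. With at most 46 evaluable patients, and 15 if the trial stops early, a non-significant p-value could sit beside an interval that excludes very little, and the plan does not require the reader to be shown that interval.

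**No account of prior-treatment group.** Treatment failures may respond less often; section 9.0 plans to look. They may also differ in expansion. The background in section 2.2 carries the heading "In Vivo Expansion Correlates With Increasing The Intensity Of The Preparative Regimen", section 2.3 relies on immunosuppressive conditioning for host acceptance of donor cells, and 4.2.2 admits patients previously given ATG+CSA or 7+3. If group relates to both variables, a pooled table can show an association that exists in neither group, or hide one that exists in both.

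This is the only planned analysis that links expansion to response. If the measure and any stratification are chosen after the data are seen, the choice is post hoc.

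**Working it through.** **1. The plan's own figure.** No number is stated for this association; its sample size comes from the Simon design in 13.1. Rejection probability is the sum over x > 5 of P(X1 = x)·P(X2 > 18 − x), with 15 patients and then 31. At 30% response this gives 0.0499, at 50% it gives 0.803, and the probability of stopping at stage 1 under 30% is 0.722. The stated 5% and 80% are reproduced. The test will therefore have 46 patients or, quite possibly, 15.

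**2. What a bare p-value hides.** Hypothetical table: 5 of 46 patients expand (about the 10% that section 2.2 reports for an earlier regimen), with responders 3/5 and 15/41.
- Chi-square = 46·(3·26 − 2·15)² / (5·41·18·28) = 105,984 / 103,320 = 1.03, p = 0.31.
- Risk difference = 0.600 − 0.366 = +23 points.
- Newcombe 95% CI, from Wilson limits 0.231 to 0.882 and 0.236 to 0.519: lower 0.234 − √(0.369² + 0.153²) = −0.17; upper 0.234 + √(0.282² + 0.130²) = +0.54.

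The p-value alone does not show that differences from −17 to +54 points remain compatible with the data.

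**3. Precision and small counts.** The approximate half-width is 1.96·√[p(1−p)(1/n₁ + 1/n₂)]. At N = 46 and 50% response it is 0.29 if 23 expand, 0.33 if 12 expand and 0.46 if 5 expand. The smallest expected count is 5 × 0.3 = 1.5 to 5 × 0.5 = 2.5 when 5 of 46 expand, and 12 × 0.3 = 3.6 when 12 expand with 30% response. At N = 15 it was under 5 in every case tried.

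**4. What pooling could do.** The documents give no expansion or response rates by prior-treatment group, so every rate here is an assumption. Take equal groups, expansion e₁ (untreated/minimally treated) and e₂ (failures), response p₁ and p₂, and no association within either group. Then:
- response in expanders = (e₁p₁ + e₂p₂)/(e₁ + e₂)
- response in non-expanders = [(1−e₁)p₁ + (1−e₂)p₂]/(2 − e₁ − e₂)

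With e = 10%/30% and p = 50%/20%: (0.05 + 0.06)/0.4 = 27.5% against (0.45 + 0.14)/1.6 = 36.9%, a spurious −9.4 points. With e₁ = e₂ the two rates are equal and there is no bias.

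Simulated rejection at nominal 5%, N = 46, no association within groups:

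| Expansion | Response | Pooled chi-square | CMH |
|---|---|---|---|
| equal in both groups | various | about 5% | about 5% |
| 10/30, 30/50 or 40/60 | 45/35 | 5.0–5.9% | about 5% |
| 10/30 | 50/20 | 6.9% | 4.7% |
| 10/50 | 50/20 | 14.0% | 4.8% |
| 50/10 | 50/20 | 16.5% | 4.6% |

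Larger assumed gaps give more: 20.4% at expansion 70/30 and response 60/20.

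**5. What stratifying costs or gains.** Power for a true +30 points, response 50/20 without expansion:

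| N | Expansion | Pooled | CMH | Conditional exact, stratified |
|---|---|---|---|---|
| 46 | 30/30 | 47% | 49% | 42% |
| 46 | 10/10 | 26% | 26% | 18% |
| 46 | 10/30 | 21% | 38% | 30% |
| 15 (8 + 7) | 30/30 | 18% | 16% | 8% |

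With equal expansion at N = 46, CMH loses nothing here; the exact version loses 47 − 42 = 5 to 26 − 18 = 8 points. At 15 patients stratifying gains nothing.

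**The case against.** **The table already holds the answer.** A chi-square test comes from a 2×2 table, from which response rates and their difference follow directly. This stands: the gap is in specification, not in data. But the plan specifies intervals for three other quantities and none for the one it says it will estimate.

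**Confounding is not shown.** A reader might infer from the background and the eligibility criteria that the pooled result is confounded. The documents do not support that. Section 9.0 plans an assessment and states no expected difference. Section 2.2 compares preparative regimens, not prior treatments, and here every patient receives the same regimen. Criterion 4.2.3 requires 4 weeks without MDS treatment before the study, and 4.7 at least 3 days off immunosuppressants before infusion. Nothing reports expansion by prior treatment. This stands in full.

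**The larger figures need large assumed gaps.** The 14.0% and 16.5% rest on a 40-point expansion gap, a 30-point response gap and an equal split. Failures were admitted only from revision 5, so an equal split is not a natural default. This stands; the figures show a range, not an expectation.

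**The remedy has limits.** An exact stratified test costs power, stratifying 15 patients is of no use, and the stratum is contradictory as written: 4.2.2 admits hypomethylating failures while 4.15 excludes them. All of this stands and shapes the fix.

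**Conclusion.** The mismatch between objective and method is certain from the text: an association is to be estimated, and only a pooled test is specified. That needs no assumption.

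On prior-treatment group, the supportable statement is that the association may be confounded and that no planned analysis would reveal or remove it. The stronger readings, that it is confounded or that the pooled test will mislead, go beyond the documents. So does reading the analysis as a test of whether expansion causes response; the objective asks only for an association.

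Size, under the assumed rates above with 23 per group: pooled rejection runs from about 5% (equal expansion, or small response gaps), through about 7%, to 14–16% for expansion of 10% against 50% in either direction. CMH stays near 5%.

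The change is worth making because it is cheap. This is a secondary analysis, and neither the Simon decision rule nor the toxicity stopping rule depends on it.

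**What to change.** Replace the chi-square sentence in 13.3 with text to this effect:

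> Response rates will be reported for patients with and without NK expansion, with the risk difference and a 95% confidence interval suited to small samples (Newcombe). An exact test will be used where expected counts are small. If the trial reaches stage 2, the Mantel-Haenszel risk difference with 95% confidence interval and the CMH test, stratified by prior-treatment group (4.2.1 versus 4.2.2), will also be reported. If the trial stops at 15 patients, only the crude risk difference and its interval will be reported.

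Before the stratum can be used, 4.2.2 and 4.15, and the matching items in the Appendix I checklist, must be reconciled. The same edit should settle when expansion is measured: 13.3 uses day +8, while section 1.3 refers to "NK cell persistence 2 weeks after infusion (Day 28").

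Cost: a short replacement in 13.3 plus that reconciliation. The checklist already records prior-treatment group, so no new data are needed. Asymptotic CMH at 46 patients costs little or no power; a conditional exact stratified test costs roughly 5 to 8 points when expansion does not differ by group. One binary stratum is about as much as 46 patients will bear.

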14.0 Conduct Of The Study

14.1 Good Clinical Practice

The study will be conducted in accordance with the appropriate regulatory requirement(s). The investigator will be thoroughly familiar with the appropriate use of the drug as described in the protocol and Investigator's Brochure. Essential clinical documents will be maintained to demonstrate the validity of the study and the integrity of the data collected. Master files should be established at the beginning of the study, maintained for the

duration of the study and retained according to the appropriate regulations.

14.2 Ethical Considerations

The study will be conducted in accordance with ethical principles founded in the Declaration of Helsinki. The IRB will review all appropriate study documentation in order to safeguard the rights, safety and well-being of the patients. The study will only be conducted at sites where IRB approval has been obtained. The protocol, informed consent, written information given to the patients, safety updates, annual progress reports, and any revisions to these documents will be provided to the IRB by the investigator.

14.3 Informed Consent

All potential study participants will be given a copy of the IRB-approved consent to review. The investigator or designee will explain all aspects of the study in lay language and answer all questions regarding the study. If the participant decides to participate in the study, he/she will be asked to sign and date the consent document. Patients who refuse to participate or who withdraw from the study will be treated without prejudice.

1.	Diagnosis of high risk MDS that meets at least one of the following disease classifications and is requiring treatment:  International Prognostic Scoring System (IPSS) Category: INT-2 or High Risk (Appendix IV)  International Prognostic Scoring System- Revised (IPSS-R) Category: High or Very High (Score of 5 or above) (Appendix IV)  WHO Classification: RAEB-1 or RAEB-2  WHO Classification: CMML that is not highly proliferative. WBC < 15K  High risk cytogenetic abnormality as defined by presence of Monosomy 7, complex karyotype, or monosomal karyotype  Therapy related MDS  Severe cytopenias: Severe neutropenia (ANC < 0.8), platelet or PRBC transfusion dependent  WHO Based Prognostic Scoring System (WPSS): High or Very High Risk (Appendix V)																						
2.	 Untreated/Minimally Treated: maximum of 2 cycles of hypomethylating agents (azacitidine or decitabine) without evidence of treatment failure as defined by progression to more advanced MDS Who classification or AML.  Treatment Failure: Patients who have not responded to or whose disease has progressed on hypomethylating agents (azacitidine or decitabine), 7+3 type induction chemotherapy, or immunosuppressive therapy such as ATG+CSA. Patients must not have received treatment for their MDS within 4 weeks of beginning the trial.																						
3.	Age ≥ 18 years of age																						
4.	ECOG Performance Status 0-2 PS - 																						
5.	Available related HLA-haploidentical NK cell donor by at least Class I serologic typing at the A&B locus																						
6.	Acceptable organ function within 14 days of study enrollment defined as: 
 
 Creatinine	≤ 2.0 mg/dL	.	//	
 
 SGOT	< 5 x institutional ULN		//	
 
 SGPT	< 5 x institutional ULN		//	
 
 oxygen saturation	≥ 90% on room air	%	//	
 
 Ejection Fraction	≥ 40% and no uncontrolled angina,	%	//	
 
 severe uncontrolled ventricular arrhythmias, or electrocardiographic evidence of acute ischemia or active conduction system abnormalities. QTc < 500 msec	Creatinine	≤ 2.0 mg/dL	 . 	  /   /  	SGOT	< 5 x institutional ULN	   	  /   /  	SGPT	< 5 x institutional ULN	   	  /   /  	oxygen saturation	≥ 90% on room air	   %	  /   /  	Ejection Fraction	≥ 40% and no uncontrolled angina,	  %	  /   /  		
Creatinine	≤ 2.0 mg/dL	 . 	  /   /  																				
SGOT	< 5 x institutional ULN	   	  /   /  																				
SGPT	< 5 x institutional ULN	   	  /   /  																				
oxygen saturation	≥ 90% on room air	   %	  /   /  																				
Ejection Fraction	≥ 40% and no uncontrolled angina,	  %	  /   /  																				
7.	Able to be off prednisone or other immunosuppressive medications for at least 3 days prior to NK cell (excluding pre-meds)																						
8.	Women of child bearing potential must agree to use effective methods of contraception (diaphragm, birth control pills, injections, intrauterine device [IUD], surgical sterilization, subcutaneous implants, or abstinence, etc.) from the time of signing the consent form and for 2 months after the last dose of chemotherapy																						
9.	Voluntary written consent																						

Decitabine and Vorinostat with CD3/CD19 Depleted Haploidentical Donor Natural Killer (NK) Cells for the Treatment of High Risk Myelodysplastic Syndromes (MDS) - MT2012-04

Eligibility Checklist – page 2 of 2

Patient initials

EXCLUSION CRITERIA

A "YES" response to any of the following disqualifies the patient from study entry.

		Yes	No
10.	Pregnant or lactating		
11.	New progressive pulmonary infiltrates on screening chest x-ray or chest CT scan that has not been evaluated with bronchoscopy (when feasible)		
12.	Uncontrolled bacterial or viral infections - chronic asymptomatic viral hepatitis is allowed		
13.	Pleural effusion moderate to large in size that are detectable on chest x-ray		
14.	Known hypersensitivity to one or more of the study agents		
15.	Prior hypomethylating treatment greater than 2 cycles or with documented treatment failure		
16.	Prior use of histone deacetylase inhibitors		
17.	Serious medical or psychiatric illness likely to interfere with participation in this clinical study in the opinion of the enrolling investigator		
18.	Inability to swallow capsules		
19.	Active HIV		
20.	Other active and potentially life threatening malignancy excluding localized basal or squamous cell skin cancer, cervical carcinoma in situ, superficial bladder cancer, localized prostate cancer		

Date consent form signed: _____

Having obtained consent and reviewed each of the inclusion/exclusion criteria, I verify that this patient is:

Eligible Ineligible Date registered _____

Signature of person verifying eligibility

Date

Appendix II - Eligibility Checklist - Donor

Decitabine and Vorinostat with CD3/CD19 Depleted Haploidentical Donor Natural Killer (NK) Cells for the Treatment of High Risk Myelodysplastic Syndromes (MDS) - MT2012-04

Eligibility Checklist – page 1 of 1

Donor initials
1st 2 initials of first name + 1st 2 initials of last name

Donor ID - -D
3 letter site code – Pt seq # (i.e. 01, 02, 03, etc.)

INCLUSION CRITERIA

A "NO" response to any of the following disqualifies the donor from study entry.

		Yes	No
1.	Related donor (sibling, parent, offspring, parent or offspring of an HLA identical sibling) 18 to 75 years of age		
2.	At least 40 kilogram body weight		
3.	In general good health as determined by the evaluating medical provider		
4.	HLA-haploidentical donor/recipient match by at least Class I serologic typing at the A&B locus		
5.	Able and willing to undergo apheresis		
6.	Not pregnant		
7.	Voluntary written consent		

Date consent form signed: _____

 Signature of person verifying eligibility

 Date

